1.1 Study design

This is a 52-week, randomized, double-blind, double-dummy, placebo-controlled, multicenter study to assess the efficacy of secukinumab 150 mg or 300 mg in patients with AxPsA who have had an inadequate response to two different NSAIDs. The study will consist of two treatment periods; a double-blind placebo-controlled period from Baseline to Week 12 followed by a double-blind secukinumab treatment period from Week 12 to Week 52.

The schematic of study design is given in Figure 1.1 below.

Planned number of patients and randomization

A total of 495 patients (165 patients per group) will be recruited to compensate dropouts and protocol violators.

Patient eligibility will be assessed during a maximum screening period of 8-weeks. At Baseline, all patients whose eligibility is confirmed will be randomized in a 1:1:1 ratio to secukinumab 150 mg, secukinumab 300 mg or placebo. At Week 12, patients randomized to placebo at Baseline will be re-randomized (1:1) to active treatment with secukinumab 150 mg or secukinumab 300 mg.

Group 1: secukinumab 150 mg

Treatment Period 1

secukinumab 150 mg (1 × 1.0 mL prefilled syringes (PFS)) + placebo (1 × 1.0 mL PFS) at Baseline, Week 1, 2, 3 and 4, then 4 weeks later at Week 8.

Treatment Period 2

secukinumab 150 mg (1 × 1.0 mL PFS) + placebo (1 × 1.0 mL PFS) administered every 4 weeks from Week 12 to Week 52 (last dose on Week 48).

Group 2: secukinumab 300 mg

Treatment Period 1

secukinumab 300 mg (2 × 1.0 mL PFS) administered at Baseline, Week 1, 2, 3 and 4, then 4 weeks later at Week 8.

Treatment Period 2

secukinumab 300 mg (2 × 1.0 mL PFS) administered every 4 weeks from Week 12 to Week 52 (last dose on Week 48).

Group 3: placebo

Treatment Period 1

placebo (2 × 1.0 mL PFS) administered at Baseline, Week 1, 2, 3 and 4, then 4 weeks later at Week 8.

Treatment Period 2

secukinumab 150 mg (1 × 1.0 mL PFS) + placebo (1 × 1.0 mL PFS) administered every 4 weeks from Week 12 to Week 52 (last dose on Week 48), OR

secukinumab 300 mg (2 × 1.0 mL PFS) administered every 4 weeks from Week 12 to Week 52 (last dose on Week 48).

[figure not shown]
Patients, investigator staff, persons performing the assessments and data analysts will remain blinded to the identity of the treatment from the time of randomization until database lock. No stratification at randomization will be performed.

Primary analysis time point

The primary and key secondary analyses will be performed at Week 12.

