2.1 Data analysis general information

The data will be analyzed by Novartis and/or by the designated CRO. It is planned that the data from all centers that participate in this protocol will be used for analysis. Analysis datasets and statistical outputs will be produced using the most recent SAS® Version 9.4 (SAS Institute Inc., Cary, NC, USA), and stored in Novartis global programming & statistical environment (GPS).

As the primary endpoint analysis will be performed at Week 12, there will be a database freeze after all patients have completed Week 12 assessments. A selected Novartis clinical team will be unblinded to the Week 12 results. Summary results may be shared internally and externally; however, individual unblinded patient data will not be disclosed. A final database lock will occur when all patients have completed the study.

Summary statistics for continuous variables will include number of patients (N), mean, standard deviation, minimum, lower quartile, median, upper quartile, maximum. Summary statistics for discrete variables will be presented in the number and percent of patients in each category. Summary statistics will also be presented graphically wherever applicable.

If not otherwise specified, p-values and confidence interval (CI) will be presented as two-sided. Unless otherwise stated, the default level of significance will be set to 5% (two-sided, family-wise type-I-error).

Data analyses will be presented by treatment group. Efficacy and safety data for the placebo-controlled period (or the entire treatment period as appropriate) will be presented by the following 3 treatment groups. Patients may be included in more than one treatment group for some analyses (e.g. exposure-adjusted adverse events over the entire treatment period).

Eligible patients will be randomized to secukinumab 150 mg (Group 1), secukinumab 300 mg (Group 2) or placebo (Group 3) for the first 12 weeks. Note that the treatment groups for a patient may differ depending on the time period of the analysis and whether one assesses the patient for efficacy or safety.

The analysis will be conducted on all patients' data at Week 12 and at the time, the trial ends (Week 52).

Comparative efficacy data

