2.4.2 Prior, concomitant and post therapies

Prior and concomitant therapies

Prior and concomitant medications will be summarized in separate tables by treatment group.

Prior medications are defined as treatments taken and stopped prior to first dose of study treatment. Any medication given at least once between the day of first dose of randomized study treatment and the date of the last study visit will be a concomitant medication, including those, which were started pre-baseline and continued into the period where study treatment is administered.

Medications will be presented in alphabetical order, by Anatomical Therapeutic Classification (ATC) codes and grouped by anatomical main group. Tables will show the overall number and percentage of patients receiving at least one treatment of a particular ATC code and at least one treatment in a particular anatomical main group.

Significant prior and concomitant surgeries and procedures will be summarized by primary system organ class and MedDRA preferred term.

The number and percentage of patients receiving prior and concomitant PsA therapy will be presented by randomized treatment group as well as the reasons for stopping their therapies (primary lack of efficacy, secondary lack of efficacy, lack of tolerability, other) and the total duration of exposure to PsA therapies previously.

In addition to that, summary of doses will also be performed for NSAID, MTX and corticosteroids. Comparison of median dose with ASAS recommendations will also be summarized.

Prior or concomitant medication will be identified by comparing recorded or imputed start and end dates of medication taken to the reference start date.

Rescue medication

Rescue medication is defined as medication used to control symptoms that are not adequately controlled on study treatment.

No patient will be restricted from receiving necessary rescue medications for lack of benefit or worsening of disease, if rescue with prohibited treatments occurs prior to completion of Week 52 assessments, patients can be discontinued from the study treatment (as per the CTT's discretion) but can continue with the study visit assessments until at least Week 12.

Rescue medication will be summarized similarly to concomitant medication.

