2.5.2 Statistical hypothesis, model, and method of analysis

The statistical hypothesis for ASAS 20 being tested is that there is no difference in the proportion of patients fulfilling the ASAS 20 criteria at Week 12 in the Secukinumab 300 mg treatment group versus placebo group.

Let p_0 denotes the proportion of ASAS 20 responders at Week 12 for placebo group and p_1 denotes the proportion in secukinumab 300 mg treatment group.

In statistical terms, the following hypothesis will be tested:

$H_0: p_1 = p_0$, versus $H_{A1}: p_1 \neq p_0$

In other words,

H_0 : Secukinumab 300 mg treatment group is not different to placebo group with respect to ASAS 20 response at Week 12

The primary analyses will be conducted via logistic regression with treatment and concomitant MTX intake status as factors. The Odds ratio, 95% confidence interval (CI) and p-value will be presented comparing secukinumab 300 mg treatment group to placebo group at Week 12.

[figure not shown]
The study is said to be positive/declared as success if the lower limit of 95% CI of odds ratio is greater than 1.

Summary statistics will also be reported for each treatment group, concomitant MTX intake status and by visit. Graphical representation will also be performed.

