Response to ASAS 40 at Week 12 will be analyzed using a logistic regression model with treatment and concomitant MTX intake status as factors. The Odds ratio, 95% confidence interval (CI) and p-value will be presented comparing secukinumab to placebo.

- **BASDAI 50 at Week 12**

BASDAI 50 response is defined as at least a 50% improvement (decrease) in total BASDAI score, as compared to the Baseline total BASDAI score.

Response to BASDAI 50 at Week 12 will be analyzed using a logistic regression model with treatment and concomitant MTX intake status as factors. The Odds ratio, 95% confidence interval (CI) and p-value will be presented comparing secukinumab to placebo.

- **Spinal pain (VAS) at Week 12**

The patient's assessment of back pain will be performed using a 100 mm VAS ranging from no pain to unbearable pain.

The mean change from baseline of spinal pain at Week 12 will be analyzed by using an ANCOVA model with treatment group, visit and concomitant MTX intake status, as factors and baseline measurement in VAS as continuous covariate. The adjusted (LS) mean difference will be calculated as a point estimate together with the corresponding 95% confidence interval and p-value.

- **SPARCC enthesitis index at Week 12**

The SPARCC enthesitis index focuses on the clinical evaluation and validation of 16 defined sites.

The mean change from baseline of SPARCC enthesitis index at Week 12 will be analyzed by using an ANCOVA model with treatment group, visit and concomitant MTX intake status, as factors and baseline SPARCC index as continuous covariate. The adjusted (LS) mean difference will be calculated as a point estimate together with the corresponding 95% confidence interval and p-value.

- **Physical function index (HAQ-DI[©]) at Week 12**

Refer to Section 2.11

- **FACIT-Fatigue[®] score at Week 12**

Refer to Section 2.11

- **ASAS Health Index at Week 12**

Refer to Section 2.11

- **ACR 20 response at Week 12**

Response to ACR 20 at Week 12 will be analyzed using a logistic regression model with treatment and concomitant MTX intake status as factors. The Odds ratio, 95% confidence interval (CI) and p-value will be presented comparing secukinumab to placebo.

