5.6.1 Secondary analyses

Categorical variables will be analyses using the logistic model, code is described above.

Endpoints with continuous data type expected to be normally distributed will be analyzed using an analysis of covariance (ANCOVA) model with treatment and baseline stratification factor, and baseline value as covariate. Confidence intervals for the difference between each dose of secukinumab and placebo will be calculated.

SAS code for ANCOVA

```
proc mixed data=aaa;
class TRT STRATA;
model response = TRT STRATA BASE / s;
lsmeans TRT / diff;
run;
```

In addition, key secondary variables measured at all post baseline visits up to Week 52 will be analyzed using longitudinal mixed effects ANCOVA model with treatment, baseline stratification factor and analysis visit as factors; and weight, baseline value, treatment by visit and baseline by visit interactions as covariates. An unstructured covariance structure will be assumed for this model. The significance of the treatment effects for secukinumab regimens at different analysis visits will be determined from the pairwise comparisons performed between secukinumab regimens and placebo at the appropriate analysis visits.

SAS code for mixed model:

```
proc mixed data=aaa;
class TRT USUBJID AVISITN STRATA;
model CHG=TRT STRATA AVISITN WEIGHT BASE TRT*AVISITN BASE*AVISITN
/ s ddfm=kr;
lsmeans TRT*AVISITN / diff cl;
repeated AVISITN / type=un subject=USUBJID;
Run;
```

In case the MMRM model does not converge the following sequential steps will be used:

1. change ddfm=kr to ddfm=bw. If still no convergence, perform step 2.
2. change type=un to type=cs. If still no convergence, perform step 3.

3. remove covariates in the following order until convergence: WEIGHT, BASE*AVISITN, STRATA.

Crude and adjusted incidence rates

The SAS codes of crude and adjusted incidence rates and confidence intervals will be referred from the MAP or AIN457F2310 M3.

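### The MTX factor in the primary model has no time point, and the SAP's only definition of concomitant runs past randomisation; define it as MTX use at baseline in text and code

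*SAP*

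**What the plan says.** SAP 2.5.2 specifies the primary analysis as "logistic regression with treatment and concomitant MTX intake status as factors". SAP 2.6.2 repeats this for the 150 mg comparison. SAP 2.7.2 uses the same factor for the binary secondary endpoints and, for spinal pain and SPARCC, an "ANCOVA model with treatment group, visit and concomitant MTX intake status, as factors". SAP 2.11 does the same for HAQ-DI, FACIT-Fatigue and the ASAS Health Index. None of these sections gives a time point for MTX status.

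The word concomitant is defined once, in SAP 2.4.2: "Any medication given at least once between the day of first dose of randomized study treatment and the date of the last study visit". The definition goes on, "including those, which were started pre-baseline and continued into the period where study treatment is administered". Continuing medication is therefore included, but the definition is not limited to it.

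The appendix uses other terms. For continuous endpoints, SAP 5.6.1 Secondary analyses has a "model with treatment and baseline stratification factor, and baseline value as covariate". The primary logistic code in 5.6.1 Primary analysis has a factor `STRATA` that is never defined. The GENMOD step, which gives the odds ratio for each imputation before pooling, adjusts for `TNFRESN` and weight and has no MTX term. SAP 1.1 states: "No stratification at randomization will be performed".

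On timing, SAP 2.1 says "there will be a database freeze after all patients have completed Week 12 assessments". The study then runs to Week 52.

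**The concern.** A covariate in a confirmatory model should be fixed before treatment can influence it. A programmer who derives the MTX factor from the only definition in the document would code a patient who starts MTX at Week 6 as a user. At the final lock, a start at Week 30 would count too, although it follows the Week 12 endpoint.

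Two things are at stake. MTX started on study may depend on both treatment and response, and adjusting for such a variable can bias the treatment odds ratio. Also, under the literal definition a patient's category is not settled when the primary analysis is run, so a later run could classify the same patient differently.

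**Working it through.** **Can the two versions of the factor differ?** They agree for patients on stable MTX at entry who continue. They differ for patients who start MTX after first dose. Table 5-1 makes an unstable MTX dose during the study (COMD07) a per-protocol exclusion only, and no entry removes an MTX starter from the FAS, on which the primary analysis is run. So the versions can differ in the primary population.

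**The plan's own figures.** SAP section 3 assumes 60% response on 300 mg, 57% on 150 mg and 40% on placebo, with 150 per group and a two-sided 5% Fisher's exact test. Full enumeration gives 92.9% power for 60% versus 40% and 82.6% for 57% versus 40%. The stated 92% and at least 80% are reproduced. No covariate enters that calculation.

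**Effect of a post-baseline factor.** The SAP gives no MTX rates, so these are assumptions: a share *m* of patients uses MTX at baseline, unrelated to response; among non-responders not on MTX, a share *s*P (placebo) or *s*A (300 mg) starts it; responders do not start. The logistic model with treatment and MTX is fitted to expected counts with 165 per arm.

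True odds ratio: (0.60/0.40) / (0.40/0.60) = 2.25.

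The odds ratios within the two MTX categories become:
- MTX no: 2.25 × (1 − *s*P) / (1 − *s*A)
- MTX yes: 2.25 × (*m* + (1 − *m*)*s*P) / (*m* + (1 − *m*)*s*A)

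If *s*P = *s*A, both stay at 2.25 and there is no bias.

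Example with *m* = 30%, *s*P = 30%, *s*A = 2%:
- MTX no: 2.25 × 0.70/0.98 = 1.61
- MTX yes: 2.25 × 0.51/0.314 = 3.65
- Common odds ratio from the fitted model: 2.14

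Other fitted values:

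| Starts, 300 mg / placebo | *m* = 30% | *m* = 50% |
|---|---|---|
| 5% / 5% | 2.25 | 2.25 |
| 5% / 15% | 2.23 | 2.24 |
| 5% / 25% | 2.18 | 2.22 |
| 2% / 30% | 2.14 | 2.20 |

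A second set with *m* from 20% to 60%, where power with a baseline factor is about 95%:

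| Starts, 300 mg / placebo | Odds ratio (true 2.25) | Power | Odds ratio under the null | Two-sided rejection under the null |
|---|---|---|---|---|
| 10% / 10% and 20% / 20% | 2.25 | 94–95% | 1.00 | 5.0% |
| 5% / 20% | 2.18–2.24 | 93–95% | 0.96–0.99 | 5.0–5.3% |
| 10% / 40% (extreme) | 2.00–2.19 | 85–93% | 0.87–0.97 | 5.2–9.3% |

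The direction follows from assuming more starts on placebo. The excess rejection under the null is in favour of placebo.

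**The case against.** The strongest reply is that SAP 2.4.2 sorts medications into summary tables and is never linked to the model factor. The appendix, where the main text has MTX status, speaks of a "baseline stratification factor", which points to baseline. The plan also expects stable MTX: Table 5-1 lists as deviations a dose not stable for at least 4 weeks before randomisation (EXCL09) and an unstable dose on study (COMD07). Baseline and on-study status should then largely coincide, and the start rates used above come from no section of the SAP.

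Much of this stands. A reader might infer that the SAP makes the factor a post-randomisation variable and that the primary test therefore conditions on post-treatment data. The document does not support that: the link between 2.4.2 and the model is an inference. A reader might also infer that the Week 12 result will fail to reproduce at the final lock. That would require the 2.4.2 definition to govern the factor, the factor to be derived again after Week 12, and patients to start MTX later. No section says the factor would be derived again.

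The reply does not close the gap. The appendix phrase does not name MTX, covers only the continuous-endpoint models, and calls the factor a stratification factor in a trial that was not stratified. The code cannot settle the matter either, since `STRATA` is undefined and the GENMOD model has no MTX term. Nothing fixes the primary model's factor at baseline.

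**Conclusion.** The point holds as a specification defect in the model that decides study success. The time of the MTX factor is not fixed, the only available definition read literally admits MTX started after randomisation, and text and code disagree on what the factor is.

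The likely numerical effect is small. In the main scenarios the odds ratio is about 2.14 to 2.24 against 2.25, and it moves only if MTX starts differ by arm. Those figures rest on assumed start rates and baseline MTX use, and on starts being commoner among placebo non-responders; the shift is then towards no effect. Only the extreme 40% versus 10% case lowers power materially. A reader might infer a raised risk of a false success for secukinumab; none of the scenarios tried shows that. The case for changing the text is that the correction is free and removes a choice from the confirmatory analysis.

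**What to change.** In SAP 2.5.2, 2.6.2, 2.7.2, 2.11 and 5.6, define the factor as MTX use at baseline (yes/no), derived from pre-dose records only. State that this variable is `STRATA` in the logistic code and in the secondary-analysis code, and drop the description of it as a stratification factor. In the GENMOD model that produces the pooled odds ratio, put this variable in place of `TNFRESN` and weight, so that the code matches the stated model. Changing `STRATA` alone would leave the pooled primary odds ratio unadjusted for MTX.

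The cost is SAP wording and a few lines of code. The definitions in 2.4.2 and the EXCL09 check already presuppose records of MTX before randomisation. The 150 per group needed and 165 per group recruited stand, because the sample size has no covariate.

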2.5.3 Handling of missing values/censoring/discontinuations

Missing data for ASAS 20 response for data up to Week 12 will be handled by multiple imputations technique.

Multiple imputation is a simulation based approach where missing values are replaced by multiple Bayesian draws from the conditional distribution of missing data given the observed data and covariates, creating multiple completed data sets. These completed data sets can then be analyzed using standard methods. Within this analysis, the ASAS composites will be imputed and response variables will be derived based on the imputed scores. In the multiple imputation analysis, the response status will be imputed based on the individual treatment arm information.

2.6 Analysis of the key secondary objective

The key secondary objective is to demonstrate that efficacy of secukinumab 150 mg s.c. is superior to placebo in the achievement of ASAS 20 response at Week 12, after primary objective is met i.e., after superiority is demonstrated for secukinumab 300 mg to placebo at Week 12.

2.6.1 Key secondary endpoint

The key secondary efficacy endpoint is the proportion of patients with ASAS 20 response in secukinumab 150 mg s.c. and placebo at Week 12.

The key secondary analyses will only be performed if superiority is demonstrated for secukinumab 300 mg to placebo at Week 12. The analysis of the key secondary variable will be based on the FAS.

2.6.2 Statistical hypothesis, model, and method of analysis

The statistical hypothesis for ASAS 20 being tested is that there is no difference in the proportion of patients fulfilling the ASAS 20 criteria at Week 12 in the Secukinumab 150 mg treatment group versus placebo group, after superiority is demonstrated for secukinumab 300 mg to placebo at Week 12.

Let p_0 denotes the proportion of ASAS 20 responders at Week 12 for placebo group and p_2 denotes the proportion in secukinumab 150 mg treatment group.

If primary objective (superiority of secukinumab 300mg to placebo) is met, the following hypothesis will be tested:

$H_0: p_2 = p_0$, versus $H_{A2}: p_2 \neq p_0$

In other words,

H_2 : Secukinumab 150 mg treatment group is not different to placebo group with respect to ASAS 20 response at Week 12

The key secondary analyses will be conducted analogous to the primary analyses, i.e., via logistic regression with treatment and concomitant MTX intake status as factors. The Odds ratio, 95% confidence interval (CI) and p-value will be presented comparing secukinumab 150 mg treatment group to placebo group at Week 12.

Summary statistics will also be reported for each treatment group and by visit. Graphical representation will also be performed.

[figure not shown]
Testing strategy

The family-wise error will be set to $\alpha=5\%$ (2-sided). H_1 is tested at α (2-sided). The graphical approach of Bretz ([Bretz et al 2009](#)) for sequentially rejective testing procedures is used to illustrate the hierarchical testing strategy ([Error! Reference source not found.](#)).

The following hypothesis will be tested sequentially and are included in the hierarchical testing strategy and type-I-error will be set such that a family-wise type-I-error of 5% is kept:

The testing sequence will continue to H_2 at α (2-sided) only if H_1 has been rejected.

Figure 2.6-1: Testing Strategy

Of note, in the description above, rejection of a hypothesis refers to rejection of the two-sided hypothesis; however, the level of a rejected hypothesis is only passed on according to the graphical procedure for the test of another hypothesis if the treatment effect is in favor of secukinumab.

